The overarching aim of the proposed program is to improve the QOL of patients who survived an episode of ARF by maximizing their cognitive, physical, and psychological recovery utilizing a mobile care coordinator. The care coordinator will bring the intervention to the patient irrespective of the patient's physical location and will be supported by an interdisciplinary team of a critical care physician, a health services scientist, an ICU nurse, and a psychologist, with input from other consultants as needed. In addition, dynamic feedback through process measurement tools and care coordination support software will inform the recovery process.³⁷⁻³⁹ We propose to evaluate the efficacy of our collaborative care intervention termed the "Mobile Critical Care Recovery Program (m-CCRP)" through a randomized clinical trial among survivors of ARF by pursuing the following specific aims:

Primary Specific Aim:

To evaluate the efficacy of m-CCRP in improving the health related quality of life of ARF survivors compared to attention control at twelve months post hospital discharge.

Hypothesis: ARF survivors randomized to twelve months of m-CCRP will have higher scores on Physical Component Summary (PCS) and Mental Component Summary (MCS) of the Medical Outcomes Study 36-item short form (SF-36),⁴⁰⁻⁴² compared to those randomized to attention control at twelve months post discharge.

Secondary Specific Aim 1:

To evaluate the efficacy of m-CCRP in improving the cognitive, physical, and psychological function of ARF survivors compared to attention control at twelve months post hospital discharge.

Hypotheses: ARF survivors randomized into twelve months of m-CCRP will have higher composite cognitive scores as assessed by the Repeatable Battery for the Assessment of Neuropsychological Status (RBANS);⁴³ higher physical performance as measured by the Short Physical Performance Battery (SPPB);⁴⁴ and lower depression and anxiety symptoms as measured by the Patient Health Questionnaire-9 (PHQ-9),^{45,46} and the Generalized Anxiety Disorder (GAD-7) scale^{47,48} than those randomized to attention control at twelve months post hospital discharge.

Secondary Specific Aim 2:

To evaluate the efficacy of m-CCRP in reducing health-care utilization by ARF survivors as compared to attention control at twelve months post hospital discharge.

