Hypothesis: ARF survivors randomized to m-CCRP will have lower health care utilization as measured by emergency department visits and re-hospitalizations, compared to those randomized to attention control.

3. Inclusion/Exclusion Criteria

Inclusion Criteria

- At least 18 years of age
- Hospitalized in the ICU
- Diagnosed with Acute Respiratory Failure (ARF) requiring greater than or equal to 24 hours of mechanical ventilation or noninvasive positive pressure ventilation or high flow nasal canula.
- Discharged to home, skilled nursing facility, sub-acute rehabilitation care, or long-term acute care
- English speaking
- Able to consent either in-person or through legally authorized representative
- Have access to a telephone

Exclusion Criteria

- Hospitalized to a regular non-ICU ward
- Diagnosis of cancer with life expectancy less than 1 year
- Admitted with ischemic or hemorrhagic cerebrovascular accident, traumatic brain injury, or undergoing neurosurgery
- History of dementing illnesses and other neurodegenerative disease such as Alzheimer's disease, Parkinson's disease, or vascular dementia (confirmed by EMR), or current prescription of anti-dementia medication, or ruled out by Functional Activities Questionnaire (FAQ) score defining dementia
- Unable to complete study questionnaire due to severe hearing loss
- Legally blind
- Pregnant (assessed by urine pregnancy test) or nursing
- Living outside the greater Indianapolis area
- Recent history of alcohol abuse > 5 drinks per day or substance abuse consistently over the last 3 months
- Status post tracheostomy and not eligible for a speaking valve
- Incarcerated at the time of study enrollment
- Schizophrenia or bipolar disorder (confirmed by EMR)
- Homelessness
- Illiterate

4. Enrollment/Randomization

Recruitment Targets:

ARF survivors will be recruited from three local tertiary care hospitals: 1) Indiana University Health Methodist, 2) University Hospital, and 3) Eskenazi Health. Recruitment from three hospitals with different demographics will increase the generalizability of our program in addition to achieving the target recruitment of enrolling 620 ARF survivors in our study.

Recruitment Procedures:

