Research staff will check the electronic medical records of ICU patients daily for eligibility. Eligible individuals (those who meet inclusion criteria and do not meet any exclusion criteria) will be screened twice per day for delirium until ICU discharge using the CAM-ICU-7. Eligible patients' primary clinical teams will be approached to confirm the eligibility. Within 48 hours of anticipated discharge, patients and/or their legally authorized representatives will be approached for study participation and enrollment.

Enrollment:

Research assistants will obtain informed consent and authorization for release of the patient's medical records, and complete the Initial Evaluation around the time of discharge. This Initial Evaluation includes quality of life (SF-36), cognitive (RBANS, MOCA), physical function (SPPB), depression (PHQ-9), anxiety (GAD-7), and sleep (ISI-7) assessments. To estimate the treatment effect in key domains, a "step-down" battery, consisting of a subset of outcome measures, will be administered when a participant is not able to tolerate the full outcome assessments. This "step-down" battery may also be administered via phone if subject is unable to complete an in-person assessment.

Randomization:

Following the Initial Evaluation, ARF survivors will then be randomized in a 1:1 manner via a computer-generated randomization scheme into m-CCRP intervention or attention control group stratified by hospital

Dual Enrollment (OPTIONAL): Patients who are eligible for and enroll in Examining Neuropsychiatric Disorders in Survivors of COVID-19 Related Critical Illness (EN-COV; IRB #11444) may be dually enrolled in this project. EN-COV is a minimal risk study. These studies contain the same study procedures at hospital discharge and 6-month time points; therefore, data will be shared across these studies for any patient who dually enrolls to ensure study visits/assessments are not duplicated. The EN-COV study will be considered the "main study" in these instances, and will have all original source documents on file for dually enrolled subjects.

5. Study Procedures

Main Components of the Mobile Critical Care Recovery Program:

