Research assistants will perform blinded in-person outcomes assessments similar to the baseline assessment using the same instruments (SF-36, RBANS MOCA, Trails A and B, SPPB, 2 minute step test, PTSS-10, employment questions, PHQ-9, GAD-7, and ISI-7) at 3, 6, and 12 . Figure 4 summarizes the study flow. We will employ multiple techniques to ensure concealment of outcomes assessment.^{91,92} Our research assistants will be trained not to inquire about study assignments. They will be conducting structured assessments that do not provide room for qualitative interviewing that should prevent unblinding. They will not be involved in study assignments and treatment administrations. Subjects will be instructed not to discuss their therapy with the research assistants. Loss of information could occur if subjects are unable to complete outcome assessments. To estimate the treatment effect in key domains, a "step-down" battery, consisting of a subset of outcome measures, will be administered when a participant is not able to tolerate the full outcome assessments. This "step-down" battery may also be administered via phone if subject is unable to complete an in-person assessment for the 3, 6 or 12 month outcomes.

Attention Control:

The study research coordinator will identify the primary care providers of patients in the attention control group and ensures appointment at the time of hospital discharge. The patients will receive a guide for ICU survivors containing phone numbers for relevant community resources, education on caregiver coping skills, and legal and financial advice. In addition, the attention control group will receive scripted phone calls by an independent care coordinator assistant not involved in any outcomes assessments. The calls frequency will be similar to the visit frequency of intervention arm (within one week post randomization) within two weeks post first phone call, afterwards twice per month for first six months, and once per month for the next six months). The phone calls will follow a script designed to ask the patients regarding their physical, cognitive, emotional and general wellbeing (see ICU survivors guide). Patients will be directed to the phone guide provided at the time of discharge. For those

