without access to the guide, the relevant phone numbers will be provided on the call and a new guide mailed within 24 hours of the phone call. We have decided upon a phone based attention control after team discussions, literature review and by our prior clinical experience.⁹³⁻⁹⁵ An in-home attention control was avoided due to the risk of diluting a care-coordinator home based intervention.

6. Reporting of Adverse Events or Unanticipated Problems

If a participant indicates suicide ideation on the PHQ-9, the patient's care team will be notified. Suicide ideation will also be reported to [name] and [name] (clinical psychiatrist working at IU Center for Aging Research) for additional follow up. Unanticipated problems will be reported according to Indiana University policy.

7. Study Withdrawal/Discontinuation

Participants who wish to withdraw from the study will notify the study team verbally during study interactions or via letter as outlined in the HIPAA authorization document.

8. Statistical Considerations

We will compare randomization results to pre-planned randomization schedule to ensure randomization integrity. To verify the comparability of the randomized groups, patients' baseline characteristics between the intervention and the usual care group will be compared using *t*-tests or Wilcoxon rank-sum tests for continuous variables and Chi-squared tests for categorical variables. All analyses will be conducted using SAS 9.4 software.

Self-reported quality of life outcomes:

Patient's health-related quality of life will be assessed using the Medical Outcome Study Short Form (SF-36). This scale has eight components (physical functioning, role-physical, bodily pain, general health, vitality, social functioning, role-emotional, and mental health) that are aggregated into a Physical Component Summary (PCS) and a Mental Component Summary (MCS).⁴⁰⁻⁴² Changes that differ between groups by 2 or more points on a scale of 0 to 100 have shown to be clinically meaningful.⁴²

Cognitive Assessment:

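### Does naming both PCS and MCS in the primary hypothesis leave the trial of 620 patients underpowered?

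*Combined protocol and SAP*

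**What the plan says.** Section 2 (Rationale and Specific Aims) sets the primary aim: "To evaluate the efficacy of m-CCRP in improving the health related quality of life of ARF survivors compared to attention control at twelve months" after hospital discharge. One hypothesis follows, that the intervention arm "will have higher scores on Physical Component Summary (PCS) and Mental Component Summary (MCS") than the control arm. Secondary Specific Aim 1, just below, opens in the plural: "Hypotheses: ARF survivors randomized into twelve months of m-CCRP will have higher composite cognitive scores", and then lists physical performance, depression and anxiety. Secondary Specific Aim 2 returns to a singular hypothesis, although it covers two measures, emergency visits and re-hospitalizations.

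Section 4 gives the "target recruitment of enrolling 620 ARF survivors in our study", and "ARF survivors will then be randomized in a 1:1 manner via a computer-generated randomization scheme", stratified by hospital. Section 5 (Outcomes Assessment) notes that "Loss of information could occur if subjects are unable to complete outcome assessments" and provides a shorter battery, by phone if needed. Section 8 says of the SF-36: "Changes that differ between groups by 2 or more points on a scale of 0 to 100 have shown to be clinically meaningful".

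The only tests named in Section 8 are for the baseline table, where "baseline characteristics between the intervention and the usual care group will be compared using" t-tests, rank-sum tests or chi-squared tests. In the text available, no success rule, alpha, 12-month model, design difference, SD, loss allowance or power accompanies the 620.

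**The concern.** Two scores joined by *and* under a single hypothesis look like co-primary endpoints that must both succeed. The plural heading of the next aim seems to confirm this by contrast. Such a rule needs no alpha adjustment, but the sample size should then rest on the probability that both tests succeed. Nothing in the text shows that 620 was chosen that way.

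If 620 was in fact sized for one score at 80% power, a program that truly helps on both could often be reported as missing its primary aim. A twelve-month trial would then end with a negative headline because of how success was defined.

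**Working it through.** **Can 620 be reproduced?** No, because its inputs are not given. The per-arm number for one score is n = 2(z₁₋α/₂ + z₁₋β)²·SD²/δ². With δ = 2 points, several unrelated sets of assumptions land close to 620:

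- SD 8, 80% power, two-sided 5%: 2 × 7.849 × 64/4 = 251.2, so 252 per arm and 504 in total. Dividing by 0.8 for 20% loss gives 630.
- SD 8.9, 80% power, two-sided 5%, no loss: 622.
- SD 10, 80% power, one-sided 5%, no loss: 620.

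None can be identified as the plan's basis.

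**Power if both scores must succeed.**

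*From the document:* 620 patients, 1:1, so 310 per arm; 2 points on each score.

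*Assumed:* two-sided 5% per score; the same residual SD for both scores; 0%, 20% or 30% loss; correlation between the two tests from −0.3 to 0.9.

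Per-score power comes from a noncentral t with noncentrality δ/(SD·√(2/n)). At SD 10 and n = 310 this is 2/0.803 = 2.49, which gives power 0.701. Joint power is the bivariate normal probability that both tests succeed at that per-score power.

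Baseline adjustment replaces SD by SD·√(1 − r²). A raw SD of 10 becomes 8 at r = 0.6, and 10·√0.51 = 7.14 at r = 0.7.

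| Residual SD | Loss | Per score | Joint (correlation −0.3 to 0.9) |
|---|---|---|---|
| 7.14 | 0% | 94% | 87–91% |
| 7.14 | 20% | 88% | 76–84% |
| 8 | 0% | 87% | 75–84% |
| 8 | 20% | 79% | 61–74% |
| 10 | 0% | 70% | 46–64% |
| 10 | 20% | 60% | 32–53% |
| 12 | 0% | 55% | 25–47% |
| 12 | 20% | 46% | 16–39% |
| 12 | 30% | 41% | 12–34% |

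If the true difference is 3 points rather than 2, with SD 10 and 20% loss, joint power is 83% to 89%.

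**Is a size adequate for one score always inadequate for two?** No. At 80% per score, joint power is 62% to 75% over the same correlations. At 90% per score it is 80% to 87%. The answer depends on the per-score power intended, which the text does not state.

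**Is the both-required rule established?** The contrast between singular and plural headings does not settle it. Secondary Aim 2 also has a singular hypothesis with two measures joined by *and*. The singular may simply mark one construct measured in two ways, and the plural in Secondary Aim 1 fits an aim that names three kinds of function.

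**Error rates.** If both scores must succeed, the chance of a false claim cannot exceed the level of a single test. If either were enough at an unadjusted 5%, the error for independent tests would be 1 − 0.95² = 9.75%. The plan does not say that either is enough.

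**The case for a change.** The strongest reply is that ambiguity in a primary hypothesis is itself a reason to act. PCS and MCS can disagree, and the text does not say what a split result would mean. Two points is the only between-group difference that the plan gives for these scores, so it is a fair benchmark. One result also holds whatever the SD, difference or loss: over the correlations used, 80% joint power needs 12% to 33% more patients than 80% power for one score.

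Much of this is correct. The ratio is sound, and the rule is indeed unwritten. But the ratio bites only if 620 was sized at 80% for one score, which is unknown. The benchmark is worded as 2 points or more, a threshold for clinical meaning, and the same sentence speaks of changes. With the SF-36 measured at baseline and at 3, 6 and 12 months, a baseline-adjusted analysis is a natural choice, and that moves the result toward the upper rows of the table. The loss that Section 5 mentions is a possibility, and the shorter battery is there to limit it.

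The reference list also ends with four entries (99 to 102) that the available text never cites, including works on missing data, survival modelling and stratified randomization. Fuller statistical text may therefore exist elsewhere, though this cannot be confirmed.

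**Conclusion.** The concern does not hold as a fault in the design. Its arithmetic reproduces, but its premise is an inference from grammar that Secondary Aim 2 undercuts. Its size depends on an SD, alpha, loss and correlation that the document does not give. With a true difference of 2 points on both scores, joint power for 620 ranges from about 12% (residual SD 12, 30% loss, correlation −0.3) to about 91% (residual SD 7.14, no loss, correlation 0.9). The plan states no power or design difference that 620 fails to deliver.

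The literal reading is also the safe one for error control. A claim made only when both scores favour the program is valid without adjustment, and any cost is in power alone. Enrolling more patients to raise joint power would be a choice about resources rather than the repair of an error.

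What stands is a gap in detail: the success rule, the alpha, the 12-month test and the basis for 620 are not written in the text available. An analyst would ordinarily settle these before unblinding and report both scores with confidence intervals. The judgement rests on the both-required reading, or some rule with controlled error, being applied. A lone score claimed at an unadjusted 5% would be a different matter, and nothing in the plan proposes it.

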The Healthy Aging Brain Care (HABC) Monitor: The HABC Monitor^{37,38} will be utilized to monitor the cognitive, physical, and psychological symptoms of patients and caregiver stress. The HABC monitor has 32 items tapping the previous four constructs (see appendix for instrument). While the total HABC Monitor score is helpful to measure change over time, each question also indicates a specific care area where help or coping strategies might be indicated. The HABC Monitor also includes questions on dangerous behaviors such as falls, home safety and automobile driving. When these cognitive, physical, or psychological symptoms will be identified, the m-CCRP team will work with the primary care clinician and other providers to begin initial pharmacological and non-pharmacological management. Hence the HABC-M will serve as a longitudinal monitoring tool that will guide the personalization of the m-CCRP care protocols to the needs of the patient at any point in time during recovery. The HABC-M will also provide dynamic feedback to allow for adaptation and customization of the intervention in real time by the care coordinator.

[figure not shown]
Study Flow:

Initial Evaluation: After enrolling subjects, the research assistants will perform blinded baseline quality of life (SF-36), cognitive (RBANS, MOCA) (Trails A and B), physical function (SPPB) 2 minute step test, post-traumatic stress syndrome questionnaire (PTSS-10), delirium experience questionnaire, depression (PHQ-9), anxiety (GAD-7), and sleep (ISI-7) assessments around the time of hospital discharge. After the randomization step, the care coordinator will contact the patients randomized into the intervention arm to start the m-CCRP intervention. Care coordinator will review hospital discharge and rehabilitation plan, identify the primary care physician, obtain the approval of the primary care to co-manage post ICU care of the eligible patients, and schedule a face-to-face visit with the patients at their place of discharge (home, sub-acute rehabilitation facility/skilled nursing facility or long-term acute care). This in-hospital step is important for relationship building and answering any concerns or queries.

The 12-month m-CCRP Intervention:

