The First Visit: The care coordinator will conduct a face-to-face encounter at the patient's residence within a week post randomization. At the selected location, the coordinator will assess the patient's cognitive, physical, and psychological status using the Mini Mental State Examination (MMSE)⁸⁶ and/or the Montreal Cognitive Assessment (MoCA) Timed up and Go test,⁸⁷ Activities of daily living (Katz scale),⁸⁸ Instrumental activities of daily living (Lawton Scale),⁸⁹ Hospital Anxiety and Depression scale (HADS),⁹⁰ and the Healthy Aging Brain Care Monitors (HABC-M).^{37,38} Caregiver stress will be noted with the HABC-M.³ The m-CCRP intervention instruments are different from the outcome assessments to ensure outcomes concealment from investigators. The coordinator will perform a community needs assessment for both the patient and the caregiver and will reconcile all prescribed and over the counter medications. The coordinator will make note of all scheduled and recommended appointments made at discharge with specialists and therapists. Initial and follow-up visits will be documented in the care coordination support software, the EMR-ABC.³⁹ (See above) Patients

and caregivers will be inquired of their personal recovery goals to be incorporated in the care plan (see below)

[figure not shown]

8

Creation of an Individualized Care Plan: Using the assessments and the information provided by the patient and the informal caregiver on the first visit, the coordinator will collaborate with the remainder of the m-CCRP team consisting of Drs. [name], [name], [name], and [name] along with the primary care to finalize the individualized care plan. Patients that may benefit from specialty care will be recommended for specialty evaluation and co-management. If necessary, the patient will be referred for a more extensive cognitive and psychological evaluation at the local mental health practices. This decision would be jointly reached by the care coordinator, the m-CCRP team members, the patient, their caregiver, and the patient's primary care provider. Finally, a second face-to-face visit *within 2 weeks* of the first visit will be arranged.

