appointments and adherence to care plans; have the patient and the caregiver complete the HABC Monitor to trigger or modify the use of specific care recovery protocols; and facilitate the caregiver's access to appropriate community resources (Figure 3). Throughout the duration of the follow-up phase, the m-CCRP coordinator will continue to work with the patients, their caregivers, m-CCRP team, and the patient's primary care and specialists to monitor, implement, and revise as necessary the individualized recovery care plan based on the prior set recovery goals. The m-CCRP team and care coordinator will meet once per week to discuss new patients and monitoring patients' progress. If a patient develops an acute illness that requires hospitalization, the team activates the acute care transition phase where the coordinator contacts the hospital team and provides them with relevant information about the patient's cognitive, physical, and psychological symptoms as well as the patient's most updated medication list. Following a hospital discharge, the coordinator will conduct a home visit within 72 hours to reconcile medications and coordinate post discharge care plan. At the end of 12 months, every patient will be transitioned to receive full care by his or her primary care provider. Figure 3 demonstrates the central role of the care coordinator with feedback from patient and caregiver, the m-CCRP team and the m-CCRP tools of HABC-M and EMR-ABC (directions of arrows show information and care plan flow).

Outcomes Assessment at 3, 6, and 12 months:

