We will use the Repeatable Battery for the Assessment of Neuropsychological Status (RBANS).⁴³ The RBANS was developed for the dual purposes of identifying and characterizing abnormal cognitive decline and a neuropsychological screening battery for adults aged 12-90 years. The entire battery takes 30 minutes to administer, and yields scaled scores for five cognitive domains (Immediate Memory, Visuospatial Construction, Language, Attention, and Delayed Memory). The RBANS has been tested and validated in neurologic, psychiatric, and healthy samples. RBANS has two versions and we will counterbalance for forms across the occasion of measurement to control for minor differences attributable to version.

Physical Performance:

Physical recovery will be assessed via the Short Physical Performance Battery (SPPB), a validated objective assessment.⁴⁴ The SPPB yields a performance score of 0-12 (0-4 poor, 5-7 intermediate, 8-12 good). A difference of 1 point indicates significant change in function.

Depression and Anxiety symptoms:

We will use the Patient Health Questionnaire–9 (PHQ-9)^{45,46} and Generalized Anxiety Disorder Scale (GAD-7)^{47,48} to determine the impact of the intervention on ARF survivors' mood and anxiety. The PHQ-9 is a nine-item depression scale with a total score from 0 to 27 and the GAD-7 is a seven-item anxiety scale with a total score from 0 to 21. Both of these scales are derived from the Patient Health Questionnaire, have good internal consistency, and test-retest reliability as well as convergent, construct, criterion, procedural and factorial validity for the diagnosis of major depression and general anxiety disorder.⁴⁵⁻⁴⁸

Acute Health Care Utilization:

In addition to patient reported emergency department and hospital admission data, we will use the local data-warehouse to capture all of the data needed to determine utilization. Furthermore, we will also use the data from the Indiana Network for Patient Care (INPC) to complement any data use outside of our health system. INPC is the primary health information exchange in the state of Indiana and it provides data for acute care services from all of the health care systems within the state of Indiana. We will determine the number of emergency department visits and the number of re-hospitalizations during follow-up as well as the diagnoses associated with each utilization episode.

Other Data Measures:

Table 7 below shows other data that will be collected.

Data Collection:

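### Does the optional MoCA at the coordinator's first visit undermine the statement that intervention and outcome instruments differ?

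*Combined protocol and SAP*

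**What the plan says.** The First Visit, in Section 5, describes a face-to-face assessment by the care coordinator within a week of randomization, in the intervention arm only. The cognitive tools offered are the MMSE "and/or the Montreal Cognitive Assessment (MoCA) Timed up and Go test", followed by the Katz and Lawton scales, the HADS and the HABC Monitor. The paragraph then states that "The m-CCRP intervention instruments are different from the outcome assessments to ensure outcomes concealment from investigators".

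The subsection on outcomes at 3, 6 and 12 months has research assistants repeat the baseline assessments "using the same instruments (SF-36, RBANS MOCA, Trails A and B, SPPB, 2 minute step test" and further scales. The baseline battery, given to everyone before randomization, also contains the MoCA: Section 5, Initial Evaluation, lists "cognitive (RBANS, MOCA) (Trails A and B), physical function (SPPB) 2 minute step test", and the Enrollment text in Section 4 agrees.

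After the first visit, the only instrument named for coordinator contacts is the HABC Monitor: the coordinator will "have the patient and the caregiver complete the HABC Monitor to trigger or modify the use of specific care recovery protocols". Control patients receive scripted telephone calls, with no cognitive test listed.

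**The concern.** The sentence is written as a safeguard, allows no exception, and is contradicted by the list in its own paragraph. Two things could be at stake. First, the treating team may hold an early score on a test that is also in the outcome battery, which is the situation the sentence says is avoided. Second, the extra test falls in one arm only and may come soon after the baseline MoCA. If scores improve with repetition, a comparison of MoCA scores between arms would favor the intervention for a reason unrelated to its benefit. Section 8 takes care over repeated cognitive testing for the RBANS ("RBANS has two versions and we will counterbalance for forms across the occasion of measurement") but says nothing comparable about the MoCA.

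**Working it through.** The plan gives no figure to reproduce here. The check is a comparison of lists and a count.

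**Instruments**

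- Coordinator's first visit (Section 5, The First Visit), 7 tools: MMSE, MoCA, Timed Up and Go, Katz, Lawton, HADS, HABC Monitor.
- Outcome battery (Section 5, Outcomes Assessment), 11 items: SF-36, RBANS, MoCA, Trails A and B, SPPB, 2 minute step test, PTSS-10, employment questions, PHQ-9, GAD-7, ISI-7.
- Instruments behind the named endpoints (Section 2 aims, Section 8), 5: SF-36 (PCS and MCS), RBANS, SPPB, PHQ-9, GAD-7. The remaining endpoint, utilization, counts emergency department visits and re-hospitalizations and uses no test.

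First visit and outcome battery share 1 item, the MoCA. First visit and endpoint instruments share 0 of 5. Katz and Lawton also appear in Table 7, but only to describe function before admission.

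**MoCA administrations, assuming the full battery is given each time**

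| | Control | Intervention |
|---|---|---|
| Baseline, 3, 6 and 12 months | 4 | 4 |
| Coordinator's first visit | 0 | 0 or 1 |
| Total through 12 months | 4 | 4 or 5 |
| Earlier MoCAs at the 3-month test | 1 | 1 or 2 |
| Earlier MoCAs at the 6-month test | 2 | 2 or 3 |
| Earlier MoCAs at the 12-month test | 3 | 3 or 4 |

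The baseline test is common to both arms and creates no difference between them. The excess is therefore at most one administration.

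**Patients who could be affected.** The target is 620, randomized 1:1, so the intervention arm has about 620 / 2 = 310. Because the coordinator may use the MMSE alone, the number with an extra MoCA lies between 0 and about 310.

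**Does the overlap reach a planned result?**

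- *Endpoints.* Section 2 names the RBANS composite as the cognitive endpoint, and Cognitive Assessment in Section 8 describes the RBANS only. The MoCA is in neither place.
- *Concealment.* What must stay hidden from the treating team is the research assistants' results. A score that the coordinator obtains within a week of randomization does not disclose a later score obtained by someone else.
- *Assessor blinding.* Section 5 protects this by other means: assessors take no part in assignment or treatment, assessments are structured, assessors are trained not to ask about assignment, and patients are told not to discuss their therapy. None depends on the two instrument lists being disjoint.

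**The case for a change.** The strongest case for a change is that the error is certain, concerns concealment, and takes one sentence to repair. The MoCA is collected at every outcome visit, and nothing in the document forbids comparing it between arms. The contents of the shortened step-down battery are not itemized, so a role for the MoCA there is neither shown nor excluded. A trial report that repeated the sentence would describe a safeguard that was not quite complete.

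The contradiction stands. It cannot be removed by reading the outcome assessments as the named endpoints only, because Section 5 lists the MoCA under that heading. The consequences are much weaker. The harm needs three things at once: an optional test is used, an unplanned comparison is made, and there is a practice effect whose size the documents do not give. Such a comparison would also include the effect of the cognitive training in the intervention (Box 1), so one extra sitting would not be the main issue in interpreting it. The contrast with the RBANS carries little weight, since its forms are counterbalanced to handle differences between versions, not practice.

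The available remedies cost more than they return. Dropping the MoCA from the first visit would alter an assessment that feeds the individualized care plan in order to tidy a sentence. Barring any between-arm use of the MoCA would give up an exploratory measure over a bias that may be zero.

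**Conclusion.** The sentence is inaccurate for the MoCA and accurate for the other six first-visit tools. It is a clerical slip, and correcting it would change no planned analysis or conclusion: 0 of 5 endpoint instruments overlap, the excess is at most one MoCA in at most about 310 patients, and neither assessor blinding nor concealment of the assessors' results depends on it. An analyst who chose to compare MoCA scores would sensibly note that intervention patients may have had one additional test; the plan need not change for that.

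This rests on three readings of the document: that the MoCA remains outside the named endpoints, that the step-down battery does not substitute the MoCA for the RBANS, and that coordinators do not repeat the MoCA later. The text schedules no such repeat, although it does not expressly rule one out.
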